#### **5.3 Implementation outcomes**

Implementation outcomes are:

1. The number of pharmacist's propositions validated by the care team;
2. The rate of pharmacist's propositions validated by the care team;
3. The number of validated propositions accepted by the participants or their relatives;
4. The rate of validated propositions accepted by the participants or their relatives;
5. The number of accepted propositions implemented within 4 months;
6. The rate of accepted propositions implemented within 4 months;
7. The drug reintroduction rate;
8. The satisfaction of the participants and the healthcare professionals, measured using ad-hoc questionnaires;
9. The perception of the intervention of participants' relatives', evaluated using an ad-hoc questionnaire;
10. The time needed to enact the whole intervention;
11. The delay between the acceptance of validated propositions by the participant and their implementation;
12. The impact of the diminution of the volume of PIMs on medications costs;
13. The cost of training healthcare professionals for the intervention.
14. The change in the burden of care for NH staff, measured using the NeuroPsychiatric Inventory – Nursing Home (NPI-NH) (Annex 6).
15. The study refusal rate at recruitment stage and the number of participants withdrawing from the study;
16. The number of calls received by of the Centre de Pharmacie Communautaire Pharmaceutical Assistance team (see section 8.1.1, page20).

---

Authorisations for the use of the EQ-5D-5L questionnaires for auto-administration and for administration by proxy have been granted by the EuroQol Group.

 Authorisation for the use of the NPI-NH questionnaire has been granted by the copyright holder.

## **5.4 Safety Outcomes**

Safety outcomes are:

1. The mortality rate, defined as the number of participant having died between baseline and completion of the follow-up period, divided by the total number of participants;
2. The hospitalisation rate, defined as the number of participant having been hospitalised between baseline and completion of the follow-up period, divided by the total number of participants;
3. The number of days spent in hospital between baseline and completion of the follow-up period;
4. The causes of hospitalisation;
5. The number of falls between baseline and follow-up;
6. The proportion of participants having experienced at least one fall;
7. The number of falls in participants having fallen at least once;
8. The number of days where restraints measures have been used.

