#### **9.2.4.7 Number of falls in participants with at least one fall**

The number of falls having occurred to participants that have fallen at least once will be computed by the investigators.

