### 11.4 Planned Analyses

#### 11.4.1 Datasets to be analysed, analysis populations

The analyses will be performed following the intention to treat approach.

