#### 11.4.3 Primary Analysis

The comparison of the primary outcome (change in number of PIMs between baseline and 4 months) between groups will be performed by means of generalised linear mixed models (GLMM), with patient representing a random effect clustered within NH and the allocation group as a fixed effect.

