#### 11.4.6 Safety analysis

At the end of the trial, all the participant-level safety outcomes will be compared between intervention groups by means of the same GLMM models mentioned above. Mortality and hospitalisation rates (NH-level) will be compared using t-tests or Mann-Whitney tests, as appropriate (see section 11.4.4).

Causes of hospitalisation will be described, but no statistical tests will be performed in this outcome.

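### Safety outcome 7 (falls among residents who fell) is tested between arms on a subset formed after randomisation; it should be descriptive, with falls conclusions resting on outcomes 5 and 6

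*Combined protocol and SAP*

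**What the plan says.** Section 5.4 has three falls outcomes among its eight safety outcomes: the fall count from baseline to follow-up (item 5), the proportion of participants with any fall (item 6), and "The number of falls in participants having fallen at least once" (item 7). Section 9.2.4.7 describes item 7 the same way: "The number of falls having occurred to participants that have fallen at least once will be computed by the investigators".

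Section 11.4.6 sets the analysis: "all the participant-level safety outcomes will be compared between intervention groups by means of the same GLMM models mentioned above". It handles mortality and hospitalisation rates separately, as nursing-home-level outcomes. It makes one exemption from testing: "Causes of hospitalisation will be described, but no statistical tests will be performed in this outcome". Item 7 is in neither group.

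The model referred to is the one in 11.4.3, "with patient representing a random effect clustered within NH and the allocation group as a fixed effect". No two-part or hurdle structure is given, and nothing cautions on how to read item 7. Section 11.4.1 states: "The analyses will be performed following the intention to treat approach".

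**The concern.** Residents are randomised at inclusion (6.2.1), and falls are counted from the baseline visit onwards. Whether someone is a faller is therefore settled after allocation, and the intervention may change it; section 4.5 makes falls a safety objective for that reason. The fallers in the two arms are not two randomised groups, and comparing them is hard to square with the stated intention-to-treat approach.

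The model does not repair this. Its only stated fixed effect is allocation, and the baseline items listed in 5.5 and 9.3.1 include no fall history.

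At stake is the reading of one safety result. If the intervention changes who falls, the mean among fallers changes because the group's composition changes. It can rise when falls are prevented and drop when falls are caused. A third falls test that may contradict items 5 and 6, with no rule on which prevails, invites misreading in either direction.

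**Working it through.** **Inputs from the documents.** Expected sample size (11.2): half of 18 homes × 59 beds × 20% = 9 × 59 × 0.20 = 106.2, which reproduces the stated 106. At 1:1 (6.2.1) that is about 53 per arm. The documents give no fall rate, effect size or margin for falls, so every fall rate below is an assumption.

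**Formula.** Mean among fallers (item 7) = mean falls per randomised resident (item 5) ÷ probability of at least one fall (item 6).

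**Assumed mix.** 70% of residents are low-risk with a Poisson mean of 0.3 falls over the 4 months, and 30% are high-risk with a mean of 2.0.

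Control arm:
- falls per resident: 0.7 × 0.3 + 0.3 × 2.0 = 0.81
- probability of a fall: 0.7 × (1 − e^−0.3) + 0.3 × (1 − e^−2) = 0.181 + 0.259 = 0.441
- mean among fallers: 0.81 ÷ 0.441 = 1.84

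Intervention arm, three patterns of benefit:

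| Rate halved in | Item 5: falls per resident | Item 6: proportion falling | Item 7: mean among fallers |
|---|---|---|---|
| nobody (control) | 0.81 | 44.1% | 1.84 |
| low-risk only | 0.105 + 0.6 = 0.705 | 0.0975 + 0.259 = 35.7% | 1.98 |
| everyone | 0.105 + 0.3 = 0.405 | 0.0975 + 0.190 = 28.7% | 1.41 |
| high-risk only | 0.21 + 0.3 = 0.51 | 0.181 + 0.190 = 37.1% | 1.37 |

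Total falls drop by 13%, 50% and 37% respectively, and items 5 and 6 show benefit every time. Item 7 rises by about 8% in the first case and drops by about 23% and 25% in the others. It also ranks the last two wrongly: the smaller reduction in falls gives the larger apparent benefit.

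**Other assumed inputs.**
- Low-risk rate halved, 80% at 0.4 and 20% at 3.0: item 7 goes from 2.03 to 2.27.
- Low-risk rate halved, 90% at 0.5 and 10% at 3.0: from 1.67 to 1.79.
- Uniform 30% reduction from 0.7 falls: no reversal, only dilution, from 1.39 to 1.27 (Poisson, about 9%) or 1.70 to 1.49 (negative binomial with k = 1, about 12%).

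**The opposite error.** Suppose controls have 6 residents with one fall and 8 with three: 6 + 24 = 30 falls in 14 fallers, mean 30 ÷ 14 = 2.14. If the intervention makes 6 more residents fall once, there are 36 falls in 20 fallers, mean 1.80. Falls rise 20% and item 7 drops 16%.

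**Size in one trial.** 5,000 trials were simulated with 53 per arm, using the 80%/20% mix with the low-risk rate halved and a Welch t-test among fallers as a simple stand-in for the GLMM. The fallers-only mean pointed to harm in 69% of trials, against 28% for the mean over all randomised residents. It was significantly harmful in 6.0% and significantly beneficial in 1.2%. With no effect, the two significant rates were 2.5% and 2.3%.

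**The case against.** The strongest reply is that the plan already contains the valid comparisons. Items 5 and 6 cover all participants and fall under the same sentence of 11.4.6. The synopsis names the number of falls among the main secondary outcomes, and that is item 5. A reader would see all three results together, and item 7 beside item 6 helps describe whether fewer residents fell or fallers fell less often. This stands, and it is why the point is minor. It supports reporting item 7; it does not support testing it.

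No decision hangs on item 7 either. There are no interim analyses (11.4.5), no statistical stopping criteria (11.3) and no margin for it, and the primary outcome does not depend on it. This also stands.

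A reader might infer that item 7 will show harm whenever the intervention prevents falls. The documents do not support that. They give no fall rates and nothing to suggest that prevention would be confined to residents who fall rarely. Two of the three patterns in the table point towards benefit. Even in the adverse simulated case a significant harm signal is uncommon, and the 69% counts only the direction of the estimate.

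Item 7 is not expressly labelled participant-level, and it could be meant as a group total. In that reading it equals the total for item 5, because non-fallers contribute zero, and the test is redundant instead of biased. The same edit resolves both readings.

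**Conclusion.** The point holds as a minor one. As 11.4.6 is worded, item 7 is compared between arms on a subset defined by a post-randomisation event that the intervention may affect. The result does not validly estimate the effect on falls, and its sign depends on which residents benefit or are harmed: from 1.84 it moves anywhere between 1.37 and 1.98 in the main example, while total falls drop throughout. Those figures rest on assumed rates and Poisson counts within risk groups. The structural point needs no particular rate. It is not a finding that the trial's falls assessment as a whole is invalid, since items 5 and 6 stand and are already planned.

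**What to change.** In 11.4.6, add item 7 to the existing exemption for causes of hospitalisation, so that it is reported by arm descriptively with no between-group test. In the same place, state that conclusions on falls rest on item 5 (all falls in all randomised participants, by a count GLMM, since 11.4.3 names no distribution) and item 6 (any fall). The definitions in 5.4 and 9.2.4.7 can stay. The cost is a sentence or two of text and one fewer safety test, with no change to data collection.

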## **5.5 Demographic information**

In order to describe the population of the study, the year of birth of participants, their gender and their date of entry in the NH will be collected.

## 6. STUDY DESIGN

### 6.1 General study design and justification of design

This study is a randomised, controlled trial of a deprescribing intervention, consisting of a pharmacist-led, deprescribing-focused medication review, resulting in the creation, validation and application of a personalized deprescribing plan by the NH care team. The study will take place in NHs already included in the intervention arm of the OLD-NH-QC-DeMo study (see section 3.1, page 13), as it aims to test the cumulative effect of the medication review and the deprescribing quality circle tested at the NH level in the QC-DeMo study. All stakeholders in the NH will have to agree for the NH to take part in the IDel study; agreement will be documented in writing (

The participants will be residents of the participating NHs which are prescribed the most drugs (see chapter 7, page 19 for details), and thus most at risk of PIM use [41-44]; if NH care team judges that discussing the possibility of deprescribing with a specific resident will destabilise her/him, this resident will be excluded from participation. The residents will be offered the option to participate in descending order of number of drugs prescribed (from most drugs prescribed to least), based on a ranking prepared by the NH pharmacist. After inclusion, participants will be randomly allocated to either the control or intervention groups, based on pre-specified, NH-specific randomisation lists (see section 6.2.1 below for details). Inclusion will continue until 20% of the residents of the NH have been included. An estimated 100 residents will be included in the study, based on a mean of 50 residents per NH and 10 NH participating in the study.

After randomisation, the record of participants allocated to the intervention group will be searched by the nurse responsible for the study in the NH ("study nurse") for clearly stated objectives of care. If no objectives are present in the record, the referent nurse for this participant will be interviewed by the pharmacist to clarify these objectives. The referent nurse will also provide a list of drugs taken by the participant without supervision of the NH staff (self-medication). Using this information and the content of the participant's records in the NH and in the pharmacy, the pharmacist will then conduct the medication review according to the formation received; the medication review process is described in chapter 8, page 20. Based on the results of the medication review, a deprescribing plan will be decided by the NH care team (head nurse, physician(s) responsible for the resident(s), and pharmacist). This plan will also include proposition for the introduction of new drugs if prescription omissions (sub-optimal treatment) are detected by the medication review. Each item of this plan will then be presented for validation to the participant or her/his representative. Once validated, baseline data collection will occur and the deprescribing plan will be implemented.

Participants allocated to the control group will receive usual care. Baseline data collection for them will occur after inclusion. Follow up data collection will occur 4 months after baseline data collection for both groups. The duration of the study will be 4 months for the participants allocated to the control group. For participants allocated to the intervention group, the realisation of the medication review by the pharmacist, the discussion of its results with the treating physicians, the creation of the deprescribing plan, and its discussion with the participant will induce a delay before baseline data collection, estimated of maximum 2 months; thus, the total duration of the study could be up to 6 months in this group. Participants allocated to both groups will be monitored as usual by the NH care team (treating physician and nurses) during and after the duration of the study. In addition, the NH care team will mention specific monitoring measures in the deprescribing plan, according to the drugs being deprescribed and the clinical situation of the participant.

### 6.2 Methods of minimising bias

#### 6.2.1 Randomisation

Participants will be randomised between the intervention and control groups at the time of inclusion, in a 1:1 ratio at the level of the NH. For each NH agreeing to participate, a randomisation list of length equal to 20% of the number of beds of the NH will be generated by the investigators, using the tool provided at [www.randomization.com](http://www.randomization.com). These lists will be created using randomly permuted blocks, to ensure a relative equilibrium between groups, even in case of incomplete inclusion in the NH. The lists will then be loaded in the REDCap randomisation module for this institution.

Allocation will be made at the end of completion of the inclusion CRF by the NH nurse (see Annex 10).

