### **7.2 Screening and recruitment**

Screening for participants will take place in the NH and will be performed by the NH care team (treating physician, head nurse and pharmacist). It will consist of two phases: ranking and screening.

Ranking: pharmacists will rank the residents in decreasing order of number of regular drugs prescribed, based on the treatment regimen recorded in the patients' file at the time of ranking.

Screening: with the ranking performed, the NH care team will decide which residents will be excluded from recruitment, as the discussion of deprescribing with them could destabilise them. After screening, a list of residents eligible for recruitment, ranked in decreasing order of PIMs use, will be prepared by the pharmacist.

Recruitment of residents will be made by the nurse responsible for the study in the NH, using the information and consent form (Annex 1 and Annex 2). Participation will initially be offered to a number of residents equal to 20% of the capacity of the NH (number of beds); residents or their representative will be given at least 24 hours of reflexion to decide whether to enter the study. For every resident declining to enter, participation will be offered to the next eligible resident, following the ranking list. Recruitment will continue until 20% of the population of the NH has been recruited, or until participation has been offered to all residents.

No compensation, monetary or otherwise, will be offered to participants.

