### **7.3 Assignment to study groups**

After recruitment, participants will be randomised between control and intervention groups. Randomisation will be made using the inclusion CRF; after randomisation, the allocation group will be recorded in a NH-specific list, to be stored with the study documents. This list will comprise the name of the

participants, their identifying code and allocated group. Allocation will be communicated to the treating physician and the participants.

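### Residents are allocated one by one from a short permuted-block list by the unblinded nurse who recruits them, and nothing requires consents to be closed or entry order to be fixed before the first allocation

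*Combined protocol and SAP*

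**What the plan says.** **Sequence (section 6.2.1).** Allocation is "in a 1:1 ratio at the level of the NH". The list is made as follows: "a randomisation list of length equal to 20% of the number of beds of the NH will be generated by the investigators". On its structure: "These lists will be created using randomly permuted blocks". No block size is given, nor whether it varies or is withheld from the homes. The lists are loaded into the REDCap randomisation module.

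**Timing and operator.** Section 6.2.1 has: "Participants will be randomised between the intervention and control groups at the time of inclusion", and then "Allocation will be made at the end of completion of the inclusion CRF by the NH nurse". Section 12.1.1 restricts data entry to the home's pharmacist and study nurse.

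**Recruitment (section 7.2).** "Recruitment of residents will be made by the nurse responsible for the study in the NH". The first batch is large: "Participation will initially be offered to a number of residents equal to 20% of the capacity of the NH". Residents or representatives have at least 24 hours to decide, with no upper limit stated. Each refusal passes the offer to the next resident on the ranking list.

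**Knowledge of earlier allocations.** Staff in the homes are not blinded (6.2.2). After randomisation the study nurse searches the records of intervention participants for care objectives (6.1). Section 7.3 adds that "the allocation group will be recorded in a NH-specific list, to be stored with the study documents". That list carries names, codes and groups.

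**Order of events.** Section 7.3 places randomisation after recruitment, without saying whether this means recruitment of one resident or of the whole home. Section 6.2.1 speaks of the time of inclusion and justifies blocking by the possibility that a home does not fill its list.

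**The concern.** Concealment has two parts. The upcoming list must be hidden, and it must not be possible to work out the next assignment from those already made. REDCap secures the first. The second is weak when one unblinded person recruits, triggers each allocation, knows the earlier ones and works through a short list balanced in blocks.

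Two routes are left open:

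- **Entry order.** The first batch of offers equals the length of the list, so several consents can be pending together. The ranking sets who is offered a place. It does not say whose inclusion form is completed first.
- **Persuasion.** If allocation has started while replacements are still being approached, the recruiter can have a view of the likely next arm during the consent conversation.

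At stake is comparability of the arms in something the trial does not measure. The primary outcome, change in the number of potentially inappropriate medications, plausibly depends on how ready the resident and team are to stop drugs. Section 5.5 collects year of birth, gender and date of entry. The only fixed effect stated for the primary model in 11.4.3 is allocation. An imbalance in readiness could not be adjusted away afterwards.

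**Working it through.** **Inputs.** Section 11.2: half of 18 homes, so 9; mean 59 beds; 20% recruited. Section 6.2.1: 1:1, permuted blocks, list length 20% of beds. Block size is an assumption, shown over 2, 4, 6 and 12.

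**The plan's own figure.** 9 × 59 × 0.20 = 106.2, which reproduces the stated 106. Mean list length is 0.20 × 59 = 11.8, about 12 slots. With the 50 beds used in the synopsis and section 6.1 it is 0.20 × 50 = 10.

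**Predictability within one block.** Let the block have 2m slots, m per arm. With a and c slots left, guessing the arm with more left is right with probability max(a, c)/(a + c). The next allocation is certain when a or c is zero. Averaging over all sequences gives:

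- expected correct guesses per block: m + ½[4^m / C(2m, m) − 1]
- expected certain allocations per block: 2m/(m + 1), a share of 1/(m + 1)

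Check by hand for a block of 4: the four positions are guessed correctly with probability 1/2, 2/3, 2/3 and 1. The sum is 2.833, and 2.833/4 = 0.708. The fourth is always certain and the third is certain with probability 1/3, so 1.333/4 = 0.333.

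| Block size | Correct per block | Share correct | Share certain | Certain per 12 | Certain of 106 |
|---|---|---|---|---|---|
| 2 | 1.5 | 75.0% | 50.0% | 6 | 53 |
| 4 | 2.833 | 70.8% | 33.3% | 4 | 35 |
| 6 | 4.1 | 68.3% | 25.0% | 3 | 27 |
| 12 | 7.716 | 64.3% | 14.3% | 1.7 | 15 |

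Pure guessing gives 50%, or 6 of 12.

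**Block size unknown.** Certainty requires knowing the block size; a good guess does not. Simulating 12-slot lists, with the guess always the arm having fewer allocations so far, gives 71.7% correct for a random mix of blocks of 2 and 4, 69.3% for 2, 4 and 6, and 68.0% for 4 and 6. Varying the block size would therefore not remove the problem.

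**What a prediction can be used for.** Setting 6.2.1, 7.2 and 7.3 side by side: the order of offers and of replacements is fixed; the order of completing inclusion forms is not. Closure of consent before the first allocation is one reading of 7.3. It does not fit well with allocation at the time of inclusion and at the end of each form in 6.2.1.

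**The case against.** The strongest case against has five parts.

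1. **The choice of order is inferred.** A reader might conclude that the nurse is given the choice of whom to enter next. No section says so. The order is unspecified, and the inclusion form in Annex 10 is not part of the text available. This stands, and the point is limited to the missing rule.
2. **Section 7.3 may already close recruitment first.** Section 1.6 also expects most participants to enter at the same time. If that is the intention, the persuasion route disappears. This stands as a possible reading, but 6.2.1 points the other way, and even then entry order remains unfixed.
3. **The motive is weakened.** Residents whom the discussion might destabilise are removed before any offer (7.1, 7.2). Teams may leave planned changes undone (7.4), and drugs may be stopped in controls (8.6). This lowers the incentive to steer without removing it.
4. **There are traces.** The result of each offer is recorded (9.2.3.11), REDCap keeps an audit trail (12.2.2) and an independent monitor reviews activity weekly (12.3). Skipping the ranking would show. Entering two pending consents in one order or the other breaks no stated rule, so there would be nothing to detect.
5. **Predictability is not bias.** Above-chance guessing is common to unblinded trials with permuted blocks. It matters only when consents are pending together or a replacement is being approached, and the recruiter has a preference. This stands in full: the percentages cannot be turned into an effect on the primary estimate.

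**Conclusion.** The point holds as a weakness of procedure. The recruiter, the person who triggers allocation and the person who knows earlier allocations are the same unblinded nurse. The list is about 12 slots long and balanced in blocks. No rule fixes entry order or clearly closes consent first. Depending on block size, from 2 to 12, the best guess is right for 75% down to 64% of entries and certain for 50% down to 14%. These figures assume that earlier allocations are tracked; the certainty figures also assume a known block size.

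Two stronger inferences are not supported. The documents do not show that allocations will be steered, and they give no basis for a size of bias. Nor do they show that the upcoming list is visible in the homes: it sits in REDCap, and only past allocations are recorded locally. The gap is worth closing because closing it is cheap and because selection at entry cannot be repaired at analysis.

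**What to change.** In sections 6.2.1, 7.2 and 7.3, state that:

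- all offers, replacements and consents in a home are completed before its first allocation;
- the inclusion forms for that home are then completed in one session, in the fixed ranking-list order.

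Section 7.2 describes the ranking first by number of regular drugs and then by use of potentially inappropriate medications. The text should say which list governs, so that the order really is fixed.

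Once consents and order are fixed, knowing an allocation during the session gives no room to act on it. Allocations need not be withheld, so allocation at the end of each form, the REDCap module and the lists all stay as they are.

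**Cost.** Protocol wording and an instruction to the homes, in place before the first allocation. Early consenters wait until their home's recruitment closes. The length of that wait cannot be computed from the documents. It matters somewhat, because the intervention group may need up to 6 months (6.1) of a 9-month study (synopsis). A few residents may change regimen, withdraw or die while waiting. As they would not yet be randomised, this costs numbers but does not unbalance the arms.
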